2.4.5.4 Analyses of vital sign variables

The summary statistics (including number, mean, median, Q1, Q3, standard deviation, minimum and maximum) of all vital signs variables (values and changes from baseline) will be calculated for each visit or study assessment (baseline, each post-baseline time point and last on-treatment) by treatment group. For all parameters, mean changes from baseline with corresponding standard error will be plotted over time in each treatment group.

The incidence of PCSAs at any time during the TEAE period will be summarized by treatment group irrespective of the baseline level and/or according to the following baseline status categories:

- Normal/missing
- Abnormal according to PCSA criterion or criteria

Listings will be provided with flags indicating the PCSA values.

2.4.5.5 Analyses of electrocardiogram variables

The summary statistics (including number, mean, median, Q1, Q3, standard deviation, minimum and maximum) of all ECG variables (central laboratory values and changes from baseline) will be calculated for each visit or study assessment (baseline, each post-baseline time point and last on-treatment) by treatment group. For all parameters, mean changes from baseline with corresponding standard error will be plotted over time in each treatment group.

The incidence of PCSAs at any time during the TEAE period will be summarized by treatment group irrespective of the baseline level and/or according to the following baseline status categories:

- Normal/missing
- Abnormal according to PCSA criterion or criteria

Listings will be provided with flags indicating the PCSA values.

2.4.6 Analyses of pharmacokinetic and pharmacodynamic variables

2.4.6.1 Analyses of serum concentrations

Concentrations of SAR440340 will be analyzed in the PK population. Concentrations of SAR440340 will be summarized in SAR440340-treated patients.

Arithmetic and geometric means, SD, standard error of the mean (SEM), coefficient of variation (CV), minimum, median and maximum per sampling time will be provided. If date and/or time of the drug injection and/or sampling is missing then the concentration will not be taken into account. Concentrations below the lower limit of quantification (LLOQ) will be set to zero for pre-dose samples (Week 0). Other concentrations below LLOQ will be replaced by LLOQ/2. Values will be expressed in the tables with no more than three significant figures.

2.4.6.2 Pharmacodynamics/genomics analyses

PD biomarkers will be analyzed in the safety population. Baseline values will be the last value collected prior to the first IMP.

For each biomarker, biomarker value, absolute change from baseline and percent change from baseline will be summarized descriptively (number, arithmetic and geometric means, SD, SEM, CV, median, minimum and maximum) by treatment group and time point. Values reported as below the LLOQ will be imputed as LLOQ/2.

Summary plots by visit for each biomarker by treatment group will be provided as:

- mean +/- standard error of the biomarker value
- mean +/- standard error of the absolute change from baseline
- mean +/- standard error of the percent change from baseline
- median(IQR) of the percent change from baseline

Exploratory analysis of DNA/RNA will be addressed in a separate document.

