9.4.3 Other analyses

PK, pharmacodynamic, and biomarker exploratory analyses are described here briefly and will be detailed in the statistical analysis plan finalized before database lock.

The population PK analysis and pharmacodynamic analyses be presented separately from the main clinical study report (CSR).

Table 16 - Other analyses

Endpoint	Statistical Analysis Methods
Pharmacokinetics (PK)	Concentrations of functional SAR440340 will be summarized using arithmetic and geometric means, standard deviation, standard error of the mean (SEM), coefficient of variation (CV%), minimum, median, and maximum by treatment per visit.
Anti-drug antibodies (ADA)	
The incidence of positive ADA response for SAR440340 will be assessed as absolute occurrence (n) and percent of patients (%), presented by treatment groups. Listing of ADA titer levels will be provided for patients positive in the ADA assay.
 
The ADA analysis will be detailed in the SAP.

Pharmacodynamics	
The values to be used as baseline will be those collected on Day 1 (predose assessments). If any of the scheduled assessments on Day 1 are technically disqualified (eg, insufficient sample), then values determined at Screening can be used as baseline.
 
For all parameters, raw data, absolute changes from baseline, and percent changes from baseline will be summarized in descriptive statistics by treatment group and time point.
 
Summary plots (mean ± standard error of the mean) on raw data, absolute changes from baseline and percent changes from baseline will be provided by treatment group.

Patient Reported Outcomes (health-related quality of life/health economics variables)	Change from baseline in the following variables: EXACT, SGRQ, and EQ-5D will be analyzed with an MMRM approach described previously for the continuous efficacy variables. Descriptive statistics including number of patients, mean, standard error and LS means will be provided. In addition, difference in LS means, the corresponding 95% CI's, and the p-values will be provided for comparison between the active treatment groups and the placebo group.

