The normalization (to ≤ 1 x ULN) or return to baseline (if baseline is >ULN) of elevated liver function tests will be summarized by categories of elevation (>3 x ULN, >5 x ULN, >10 x ULN, >20 x ULN for ALT and AST, >1.5 x ULN for alkaline phosphatase, and >1.5 x ULN and >2 x ULN for total bilirubin) with the following categories of normalization: never normalized, normalized despite treatment continuation of IMP, or normalized after IMP discontinuation. A patient will be counted only under the maximum elevation category.

Change in Blood Eosinophil

Absolute and percent mean (median) change from baseline in eosinophil count will be summarized and plotted over time in each treatment group for patients with baseline blood eosinophil <0.25 Giga/L and patients with baseline blood eosinophil ≥ 0.25 Giga/L.

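### SAP 2.4.6.2 asks for geometric means and CVs of biomarker changes from baseline; those entries will be undefined or misleading, though the rest of the PD summary stands

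*SAP*

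**What the plan says.** SAP 2.4.6.2 (Pharmacodynamics/genomics analyses) takes the biomarker value together with its changes and gives them all the same statistics: "For each biomarker, biomarker value, absolute change from baseline and percent change from baseline will be summarized descriptively (number, arithmetic and geometric means", and then the SD, standard error, CV, median and extremes. The summaries are by treatment group and time point. Nothing limits the geometric mean or the CV to the values, and there is no rule for a negative or zero change. For low assay results the section says "Values reported as below the LLOQ will be imputed as LLOQ/2".

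The section also plans four plots by visit. Three show an arithmetic mean with its standard error, for the value, the absolute change and the percent change (the last being "mean +/- standard error of the percent change from baseline"). The fourth is "median(IQR) of the percent change from baseline".

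Three neighbouring texts help with interpretation:

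- Protocol 9.4.3, Table 16, plans the same summary without naming a geometric mean: "raw data, absolute changes from baseline, and percent changes from baseline will be summarized in descriptive statistics by treatment group and time point".
- SAP 2.4.5.3 has a separate eosinophil summary based on mean and median only: "Absolute and percent mean (median) change from baseline in eosinophil count will be summarized and plotted over time in each treatment group".
- SAP 2.4.6.1 has almost the same list for drug concentrations, where it is valid: "Arithmetic and geometric means, SD, standard error of the mean (SEM), coefficient of variation (CV), minimum, median and maximum per sampling time will be provided".

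**The concern.** The geometric mean is exp(mean of ln x), so every x must be above zero. A biomarker value meets that condition. A change from baseline does not: even with no drug effect, about half the patients fall. Protocol 8.3.1, Table 6, says that SAR440340 inhibits Th2 cytokine production, so falls are plausible for at least some markers.

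A programmer who follows the text has two options. The cell can be left missing, or non-positive changes can be set to missing when logs are taken. The second option gives an average over only the patients whose marker rose, which is positive by construction in both arms and could be read as a rise on active drug.

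The CV has a related problem. It divides the SD by the mean, so it explodes when the mean change is near zero and turns negative when the mean change is negative.

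At stake is the readability of the change tables for eosinophils, neutrophils, total IL-33, sST2, calcitonin, PARC, eotaxin-3, IgE, fibrinogen and FeNO.

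**Working it through.** The documents state no figure for these summaries, so there is nothing to reproduce. The check asks whether the statistics are defined and then illustrates what happens if they are forced.

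**1. A small worked case (invented numbers).** Take percent changes {-40, -30, -20, 0, 10}.

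- ln is undefined for the three negatives and minus infinity for 0, so the geometric mean cannot be computed.
- Dropping non-positive values leaves only 10, so the entry would read +10.
- The arithmetic mean is -80/5 = -16 and the median is -20.
- SD = sqrt((24² + 14² + 4² + 16² + 26²)/4) = sqrt(1720/4) = 20.7, so CV = 20.7/(-16) = -130%. Adding 16 to every value leaves the SD unchanged and makes the mean 0, and the CV is then a division by zero.

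**2. Does the LLOQ rule help?** It keeps assay values positive but not changes. If baseline and visit are both below LLOQ, the change is LLOQ/2 - LLOQ/2 = 0, which creates a zero.

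**3. How often does the problem arise?** Assumptions, none from the documents: log-normal marker, baseline median 200 and log-SD 0.6, log-SD *s* of the post/baseline ratio 0.3 or 0.5, true geometric mean ratio *R*. The share of changes at or below zero is Φ(-ln R / s). For R = 0.7, s = 0.3 this is Φ(0.357/0.3) = 88%; for s = 0.5, Φ(0.357/0.5) = 76%. A simulation of 200,000 patients agrees. Each cell shows s = 0.3 / s = 0.5:

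| True R | Share ≤ 0 | Arithmetic mean % change | Median % change | Geometric mean, positive changes only | Geometric mean ratio, as % change |
|---|---|---|---|---|---|
| 1.0 | 50% / 50% | +4.5 / +13.3 | 0.0 / +0.1 | +17.9 / +32.5 | -0.1 / 0.0 |
| 0.9 | 64% / 58% | -5.9 / +2.1 | -10.0 / -9.8 | +14.6 / +28.5 | -10.0 / -9.8 |
| 0.7 | 88% / 76% | -26.7 / -20.6 | -30.0 / -29.9 | +9.7 / +21.4 | -30.0 / -29.9 |
| 0.5 | 99% / 92% | -47.7 / -43.3 | -50.0 / -50.0 | +6.4 / +15.4 | -50.0 / -50.0 |
| 1.5 | 9% / 21% | +57.1 / +70.2 | +50.0 / +50.2 | +46.0 / +59.0 | +50.2 / +50.1 |

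With the planned 170 patients per arm, the probability that every change in an arm is positive is at most 2 × 10⁻⁷ in any of these scenarios (highest at R = 1.5, s = 0.3).

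**4. Sensitivity to the assumed variability.** If 0.3 to 0.5 is instead the log-SD of each measurement, the log-ratio SD is √2 times larger, 0.42 to 0.71. At R = 0.7 the non-positive share is then 69% to 80%, the positive-only geometric mean +17% to +37%, and the arithmetic mean -23% to -10%. At R = 1.0 the last two are +27% to +51% and +9% to +28%. The sizes move; the wrong sign at R = 0.7 does not.

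**The case against.** The strongest reply is that the flaw is confined and the output around it is sound. The list also requires n, arithmetic mean, SD, SEM, median, minimum and maximum, all valid for negative changes, and none of the four plots uses a geometric mean. The planned geometric means of values even let a reader form visit/baseline, which equals the geometric mean ratio when the same patients contribute to both. Pharmacodynamics sits under tertiary/exploratory objectives in Protocol Table 1, the analysis is descriptive, and Protocol 9.4.3 has it presented separately from the main study report. All of this stands, and it limits the impact.

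It also rules out three stronger readings that a reader might infer:

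- *The PD summary as a whole fails.* It does not. Only the geometric mean and CV entries for the two change variables break.
- *A fall would be hidden.* The median percent change is already in the table and in a plot. In the illustration it shows -30% when the true fall is 30%.
- *The arithmetic mean percent change understates the drug effect.* Within one arm it is pulled upward by skew, but the trial has a placebo arm. At R = 0.7 against R = 1.0, the ratio of (1 + mean change) is 0.733/1.045 = 0.70 for s = 0.3 and 0.794/1.133 = 0.70 for s = 0.5. The inflation factor exp(s²/2) cancels if within-patient variability is the same in both arms.

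Nor do the documents say that non-positive changes will be dropped. That is one possible programming outcome; a missing cell is the other.

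What the reply does not remove is that the SAP text specifies an entry that cannot be computed. The close match with the concentration list in SAP 2.4.6.1 suggests a list carried over from a setting where it was valid, but that is inference, and the text needs correcting either way.

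**Conclusion.** The point holds in a narrow form. SAP 2.4.6.2 prescribes a geometric mean for absolute and percent change, and that statistic is undefined for the negative and zero changes that can be expected in both arms. It also prescribes a CV for these changes, which loses meaning when the mean change is near zero or negative. This follows from the definitions and needs no distributional assumption.

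The size of any misleading entry does depend on assumptions. Over the variability considered, a true 30% fall would give a positive-only geometric mean of +10% to +37%, and no true change would give +18% to +51%. The documents give no biomarker distribution, so these figures are illustrations only.

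The consequence is limited: no primary or secondary endpoint, hypothesis test or sample size depends on these cells. It is a correction to make before the tables are programmed, not a threat to the trial's conclusions.

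**What to change.** In SAP 2.4.6.2:

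1. Restrict the geometric mean and CV to biomarker values.
2. For change, report by visit and arm the geometric mean of the post/baseline ratio, exp(mean of ln(post/baseline)), shown as 100 × (ratio - 1) with a 95% CI. Unlike the quotient of the two planned geometric means, this uses the same patients at both times and carries an interval.
3. State a floor for cell counts reported as zero, so that logs are defined for eosinophils and neutrophils. The LLOQ/2 rule already does this for assayed markers.
4. Keep the arithmetic mean, SD, SEM, median, minimum and maximum of the changes, and all four plots.

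A SAR440340/placebo ratio of these geometric mean ratios, or a ratio-scale plot, would be a useful extra but is not needed to repair the text.

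The cost is minor SAP wording and table-shell edits, with no additional data. The one choice to make is the floor for zero counts, which should be fixed before unblinding.

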2.4.7 Analyses of ADA variables

2.4.7.1 Analysis of ADA bioanalytical data

Analyses described in this section will be performed for ADA against SAR440340.

ADA response categories and titer categories are defined as follows:

ADA response categories

- **Pre-existing immunoreactivity:** defined as either an ADA positive response in the assay at baseline with all post first dose ADA results negative, OR a positive response at baseline with all post first dose ADA responses less than 9-fold over baseline titer levels.
- **Treatment-emergent response:** defined as a positive response in the ADA assay post first dose when baseline results are negative or missing. A treatment-emergent response is further classified as persistent, indeterminate or transient:
 - **Persistent response:** treatment-emergent ADA response detected at 2 or more consecutive ADA positive sampling time points, separated by at least 16-week period (based on nominal sampling time) with no ADA negative samples in between.
 - **Indeterminate response:** treatment-emergent response when only the last collected sample is positive.
 - **Transient response:** a treatment-emergent response that is not persistent or indeterminate.

- **Treatment-boosted response:** defined as a positive response in the ADA assay post first dose that is greater than or equal to 9-fold over baseline titer levels, when baseline results are positive.

Patients will be classified as ADA positive patients and ADA negative patients. ADA positive patients are the patients with treatment-emergent or treatment-boosted response, and ADA negative patients are patients with pre-existing immunoreactivity or negative in the ADA assay at all time points.

Maximum Titer categories

- **Low** (Titer<1000)
- **Moderate** (1000≤Titer≤10000)
- **High** (Titer>10000)

The following summaries will be provided based on ADA population:

Baseline summary:

- Number (%) of patients with a positive response in the ADA assay at baseline
 - Summary statistics (including number, median, Q1, Q3, minimum and maximum) of titer for patients with a positive response
- Number (%) of patients with a negative response in the ADA assay at baseline

Post-baseline summary:

- Number (%) of patients with pre-existing immunoreactivity
- Number (%) of patients with treatment-emergent ADA response
 - Number (%) of patients with persistent response
 - Number (%) of patients with indeterminate response
 - Number (%) of patients with transient response
- Number (%) of patients with treatment-boosted ADA response
- Number (%) of ADA positive patients
- Number (%) of ADA negative patients

Listing of all ADA titer levels will be provided for patients with treatment-emergent and treatment-boosted responses.

2.4.7.2 Association of immunogenicity with exposure, safety and efficacy

The potential association between key ADA variables (ADA positive, persistent ADA and titer) and exposure will be explored. Association between ADA and safety/efficacy may be explored depending on the number of patients positive in the ADA assay.

Association between ADA and impact on drug concentration profile

Association between key ADA variables and systemic exposure to study drug will be explored. Descriptive summary of functional SAR440340 concentrations will be provided by anti-SAR440340 antibody patient classification in SAR440340-treated patients at each visit. In addition, plots of drug concentration may be provided for analyzing the potential impact of ADA on PK.

Association between ADA and safety

Association of safety versus key ADA variables may be explored. The safety assessment may focus on the following events:

- Injection site reaction (serious or severe and lasting 24 hours or longer)
- Hypersensitivity reactions
- Anaphylactic reactions

Number (%) of patients with these events may be summarized by ADA patient classifications.

Association between ADA and efficacy

Association between the key ADA variables and key efficacy endpoints may be explored. The following efficacy endpoints may be analyzed by ADA patient classifications:

- Annualized rate of moderate or severe AECOPD
- Mean change from baseline in pre-BD FEV1 to Weeks 16-24

2.5 DATA HANDLING CONVENTIONS

2.5.1 General conventions

Demographic formulas

- Age of onset of COPD is calculated as:

$$\text{Year of diagnosis of COPD} - \text{Year of birth}$$

- Time since first diagnosis of COPD (years) is calculated as:

$$(\text{Year of randomization} - \text{Year of first diagnosis of COPD}) + (\text{month of randomization} - \text{month of first diagnosis of COPD}) / 12$$

- Time since cessation of smoking (years) is calculated as:
 $(\text{Year of randomization} - \text{Year of cessation}) + (\text{month of randomization} - \text{month of cessation})/12$
- Time since last COPD exacerbation (months) is calculated as:
 $(\text{Year of randomization} - \text{Year of last COPD exacerbation}) \times 12 + (\text{month of randomization} - \text{month of last COPD exacerbation})$
- BMI is calculated as:
$$\text{Weight in kg} / (\text{height}^2 \text{ in meters})$$
- Smoking quantity (pack-year) is calculated as following:
$$\text{Number of pack-year} = (\text{packs smoked per day}) \times (\text{years as a smoker})$$

Renal function formulas

Creatinine clearance (CrCl) value will be derived using the equation of Cockcroft and Gault:

$$\text{CLcr (ml/min)} = (140 - \text{age}) \times \text{weight (kg)} \times (1 - 0.15 \times \text{sex (0-M, 1-F)}) / (0.814 \times \text{creatinine } (\mu\text{mol/l}))$$

CLcr will be calculated using the last weight measurement on or before the visit of the creatinine measurement and age at the lab sampling date. Here age is calculated as following:

$$\text{Integer part of } (\text{Lab sampling date} - \text{Date of screening visit}) / 365.25 + \text{Age at screening visit}$$

2.5.2 Data handling conventions for other efficacy variables

The number of salbutamol/albuterol or levosalbutamol/levalbuterol inhalations per day is the number of inhalations recorded in one diary day including the evening diary and the following day's morning diary.

For the daily efficacy endpoints (eDiary, home spirometry, actigraphy), the time period used to calculate the periodical average at each study visit day is fourteen (14) days before the visit.

[Table 8](#) summarizes the time periods corresponding to each study day and week.

Table 5 - Periodical average of daily efficacy assessment

Time point Day/Week	eDiary data, Actigraphy (daily activity), home spirometry	Number of inhalations/day of salbutamol/albuterol or levosalbutamol/levalbuterol
Day 1/Randomization	Screening-Day -1	Screening-Day -1
Day 15/Visit 3	1-14	Diary Day 1-14
Day 29/Visit 4	15-28	Diary Day 15-28
Day 43/Visit 5	29-42	Diary Day 29-42
Day 57/Visit 6	43-56	Diary Day 43-56
...
Day 141/Visit 10	127-140	Diary Day 127-140
...
Day 365/Visit EOT	351 - 364	Diary Day 351 - 364

2.5.3 Missing data

For categorical variables, patients with missing data are not included in calculations of percentages unless otherwise specified. When relevant, the number of patients with missing data is presented.

Handling of computation of treatment duration if investigational medicinal product end of treatment date is missing

For the calculation of the treatment duration, the date of the last dose of IMP is equal to the date of last administration reported on the end-of-treatment case report form page. If this date is missing, the exposure duration should be left as missing.

The last dose intake should be clearly identified in the case report form and should not be approximated by the last returned package date.

Handling of medication missing/partial dates

No imputation of medication start/end dates or times will be performed. If a medication date or time is missing or partially missing and it cannot be determined whether it was taken prior or concomitantly, it will be considered a prior and concomitant medication.

Handling of adverse events with missing or partial date/time of onset

Missing or partial adverse event onset dates and times will be imputed so that if the partial adverse event onset date/time information does not indicate that the adverse event started prior to treatment or after the treatment-emergent adverse event period, the adverse event will be classified as treatment-emergent. No imputation of adverse event end dates/times will be performed. These data imputations are for categorization purpose only and will not be used in listings. No imputation is planned for date/time of adverse event resolution.

Handling of adverse events when date and time of first investigational medicinal product administration is missing

When the date and time of the first IMP administration is missing, all adverse events that occurred on or after the day of randomization should be considered as treatment-emergent adverse events. The exposure duration should be kept as missing.

Handling of missing assessment of relationship of adverse events to investigational medicinal product

If the assessment of the relationship to IMP is missing, then the relationship to IMP has to be assumed and the adverse event considered as such in the frequency tables of possibly related adverse events, but no imputation should be done at the data level.

Handling of missing severity of adverse events

If the severity is missing for one of the treatment-emergent occurrences of an adverse event, the maximal severity on the remaining occurrences will be considered. If the severity is missing for all the occurrences, a “missing” category will be added in the summary table.

Handling of potentially clinically significant abnormalities

If a patient has a missing baseline he will be grouped in the category “normal/missing at baseline.”

For PCSAs with 2 conditions, one based on a change from baseline value or a normal range and the other on a threshold value, with the first condition being missing, the PCSA will be based only on the second condition.

For a PCSA defined on a threshold and/or a normal range, this PCSA will be derived using this threshold if the normal range is missing; eg, for eosinophils the PCSA is > 0.5 GIGA/L or $>ULN$ if $ULN \geq 0.5$ GIGA/L. When ULN is missing, the value 0.5 should be used.

Measurements flagged as invalid by the laboratory will not be summarized or taken into account in the computation of PCSA values.

